### **C. Objective Cough Monitoring:**

Participants will be asked to wear an ambulatory cough monitor (VitaloJAK™, Vitalograph, UK) for 24 hours, 3 times during the study: Visits 2, 5 and 8. This involves attaching an air microphone to the lapel of the clothing and a chest sensor on the sternum. The VitaloJAK cough recorder is worn around the waist of the subject. Subjects will wear the cough monitor for a continuous 24 hours and return the following day for the procedures for the next visit. Subjects will be informed not to have a shower during this period to prevent the air microphone and chest sensor being damaged by water.

The VitaloJAK cough monitor is a non-invasive, battery operated, and custom-built validated recording device and microphone intended to acquire, record and store ambulatory cough sounds from participants for 24 hours. Briefly, this consists of a digital data logger recording sounds at a sample rate of 8 kHz, with 16-bit resolution and in Waveform Audio File format, which is a commonly used uncompressed sound file format. Recordings will be transferred to a personal computer; silences and background noise will be removed by using validated, custom-written software, and cough sounds will be counted by using an audio editing package. The number of coughs will be expressed as coughs per hour and added up to give a cough count for a 24-hour period, awake cough frequency, and night-time cough frequency.

The cough monitor is an audio recording device and will record all sound including conversations. The cough monitor microphones capture speech in the local vicinity in addition to cough sounds. Therefore, it is possible that despite processing of the cough recording by customised software, some of the participant’s conversations are also

captured in addition to their cough sounds. The recordings will be processed using an algorithm which compresses the recording and removes any non-cough sounds. On occasion the recordings may capture non-cough sounds which will require sound analysis by a cough analyst. The recordings will be sent outside of McMaster to be processed by an analyst who will be bound by a strict duty of confidentiality not to disclose any information heard. A central analyst is required for data consistency and accuracy. Vitalograph Ltd. ([name]) will act as the external vendor responsible for processing the cough monitor audio recordings. Prior to enrolment in the trial, this possibility will be explained to the subjects. Any conversations recorded would be treated with the usual standards of confidentiality as per GCP guidelines. Confidentiality will be maintained so long as the analyst does not hear any recordings suggesting the participant may harm themselves or someone else. The cough monitor has a mute button to allow sensitive personal conversations to be muted. If any personally sensitive information become apparent during the cough counting process, then these will be deleted out.

#### **D. Methacholine Challenge Test**

Methacholine is a synthetic form of acetylcholine and therefore causes smooth muscle contraction. It is commonly used in clinical practice to exclude asthma, but also as a measure of airway hyper-responsiveness. It involves giving nebulised methacholine in doubling concentrations from 0.0625 mg/mL up to 16 mg/ml via the 2-minute tidal breathing method. At each concentration, FEV1 is measured 30s and 90s after the end of each inhalation. The % fall in FEV1 from baseline is calculated after each dose using the best FEV1 and the test is terminated once a 20% fall in FEV1 (PC20) is documented or the maximum concentration of 32 mg/mL is reached. Patients with a methacholine PC20<16mg/ml will be considered to have asthma. The methacholine PC20 will be assessed at Visit 1 and Visit 9. Information about which medication to stop prior to the test will be given to the patient.

#### **E. Sputum Induction:**

Prior to performing the sputum induction, spirometry will be repeated to ensure FEV1 has returned to within 10% of the baseline prior to the methacholine challenge test. This may require 200-400mcg of salbutamol in addition to the post-methacholine challenge test salbutamol. The purpose is to induce sputum from the airways by giving nebulised hypertonic saline (3%/5%/7%) in incremental doses for a 7 min interval, provided the FEV1 does not fall by more than 20% drop from pre-sputum baseline. If there is a drop in FEV1 between 10-20% then a lower saline concentration (0.9%, 3%, 5%) will be administered. If the FEV1 drops by  $\geq 20\%$  then sputum induction will be stopped and salbutamol via inhaler or nebuliser will be given to bring the FEV1 to at least 90% of the baseline pre-sputum FEV1. Once sputum is collected in a sterile pot, it will be put on ice and sent to the laboratory for total, differential cell count, eosinophil free granules. Remaining cells from sputum processing on Visits 3 and 9 will be used to determine total and activated mature eosinophils by flow cytometry. Remaining supernatant from sputum processing at Visit 1 will be stored and used to analyse neuro-inflammatory cytokines and protein biomarkers at a later date.

## F. Questionnaires:

### *i) Ontario Covid-19 Assessment Tool and Information Letter*

In light of the current global COVID-19 pandemic, Canadian public health authorities have strongly recommended that everyone take additional precautions, including those outlined in the Information Letter, which will be provided to every participant via email before they start this study, and in person at every visit to the research laboratory. This Information Letter will be signed by each participant at every visit before any procedures take place. The day before, and one hour before every study visit, a member of the study team will ask each participant to complete the Ontario Covid-19 self-assessment tool and confirm that the result indicates that “you do not seem to have symptoms or be part of an at-risk group”, using the participants preferred contact method (phone, text, email). If this is not the case, the participant will be asked to contact the research team to reschedule their appointment. McMaster University is attempting to limit the risk of exposure to COVID-19 by using reasonable efforts to follow the health and safety guidelines recommended by the provincial and federal health authorities. Nevertheless, there

remains a risk that by attending McMaster University campus or any of the McMaster University study sites, the participant may contract COVID-19. COVID-19 can result in severe illness, medical expenses, loss of income and death.

*ii) The Leicester Cough Questionnaire* is a patient-reported questionnaires conducted on Visits 1, 3, 4, 6, 7 and 9. The LCQ is a 19-item questionnaire on a 7-point Likert scale ranging from 1 (all of the time) to 7 (none of the time) used to assess the impact of chronic cough on patients using a recall period of 2 weeks. The 19 questions assess impact on psychological, social and physical domains (Appendix 1).

*iii) The modified Borg Scale* is a patient-reported questionnaire reported on Visits 1, 3, 4, 6, 7 and 9 and will be used to assess the intensity of sensations and self-perceived cough severity related to cough over a 2-week period; cough severity, urge to cough, throat itch, tickle, and irritation. The scale ranges from 0-10, where words are linked with numbers on a logarithmic scale (Appendix 2).

*iv) The Cough Severity Visual Analogue Scale (0-100mm)* is a single item that assesses a patient's severity of cough over a recall period of 1 week using a 0 to 100mm horizontal visual analogue scale (VAS). Participants will rate their severity of cough on the scale which has a minimum value of 0 equalling "no cough" and a maximum value of 100 equalling "worst cough". A higher score indicates greater cough severity.

**Table 1.** Visit and procedure schedule.

Visit	1	2	3	4	5	6	7	8	9
Study Day	1	$13 \pm 7^*$	$14 \pm 3^{\dagger}$	$42 \pm 3^{\dagger}$	$70 \pm 3^{\dagger}$	$71 \pm 3^{\dagger}$	$99 \pm 3^{\dagger}$	$113 \pm 7^{\dagger}$	$114 \pm 3^{\dagger}$
Post-Randomization	-14	-1	0	28	56	57	84	98	99
Week	-2		0	4	8		12	14	
Procedure									
Ontario Covid-19 Assessment Tool	X	X	X	X	X	X	X	X	X
Informed Consent	X								
Medical History	X								
Adverse Events		X	X	X	X	X	X	X	X
Prior and Con Meds		X	X	X	X	X	X	X	X
Examination	X								
Vital Signs	X	X	X	X	X	X	X	X	X

Urine B-HCG ¥	X		X	X	X		X		
Spirometry	X		X			X			X
Cough Monitoring		X			X			X	
Methacholine PC 20	X								X
Induced Sputum	X #		X			X			X
Blood Sampling	X		X	X		X	X		X
LCQ	X		X	X		X	X		X
mBorg Scale	X		X	X		X	X		X
Cough Severity VAS	X		X	X		X	X		X
Mepolizumab/Placebo			X	X	X		X		

\* May be shortened to 7 days or extended to 21 days depending on availability of sputum cell counting to confirm eligibility of sputum eosinophilia >2%.

†Flexibility provided to allow visits cough monitoring on Friday and subsequent visit on Monday.

¥ Urine pregnancy test will be done for women of childbearing potential (WOCBP) prior to administration of IP.

#Sputum induction at visit 1 could be repeated after 24-48 hours if insufficient sample at visit 1.

#### 5.11.1. Safety of Study procedures

Methacholine challenge testing has been used extensively both as a clinical tool in diagnosing asthma but also as a research tool to measure airway hyper-responsiveness. Methacholine acts directly on bronchial smooth muscle and causes bronchoconstriction. Most patients have no symptoms at all or transient symptoms whilst performing this challenge which improve within 24 hours. In a 1000 patient multi-centre COPD trial using methacholine challenge, 25% had cough, 21% had dyspnoea, 10% had wheezing, 6% had dizziness, and 2% had headache after the test, with two-thirds reporting no symptoms. They were asymptomatic on leaving the trial centre on the visit day and only 0.3% had symptoms such as chest soreness in the days after the test (32).

Vlachos-Mayer H et al (33) retrospectively analyzed the safety of sputum induction in 304 patients with asthma and 25 with smoking related chronic airflow obstruction. Sputum induction protocols varied according to baseline FEV1 (<70% or ≥70%) but they found it was safe even amongst patients with an FEV1 of <60% and <1 L, provided that safety precautions similar to that of methacholine challenge testing are taken. Fahy et al (34) also showed the safety and reproducibility of combining methacholine challenge testing with sputum induction immediately afterwards twice within 1 week with moderate to severe asthmatics. Furthermore, Mulder et al

(35) showed repeatedly performing sputum induction at 4, 7 and 24hrs after a MCT was safe and well tolerated.

### **5.12. Washout Period**

This study does not have a washout period because this is a parallel group study design.

### **5.13. Blinding and Randomization**

Subjects will be assigned to one of the two possible treatment arms generated by a computer-generated randomisation schedule prepared by McMaster University, with a ratio of 1:1, mepolizumab or placebo. As there is a known imbalance in the prevalence and cough rates, the study will include sex as a randomisation factor. This will mitigate the possibility of the intervention being confounded by sex differences in the 2 arms of the study. Blinded study drug supplies will be provided in sequentially numbered identical syringes in accordance with the randomisation schedule and dispensed by a pharmacist who shall not be delegated any other role in the study. Subjects, investigators, research staff (with the exception of the pharmacist) and the sponsor will be masked to the treatment sequence assignment. A sealed code-break envelope for each subject containing details of the treatment allocated will be kept in a locked safe at the study site.

### **5.14. Premature Withdrawal/Discontinuation Criteria**

During the process of informed consent, participants will be informed that they may withdraw from the study at any time voluntarily without giving any reason and without their medical care or legal rights being affected. If a participant decides to withdraw from the study early, the data collected will be retained with their permission. If the participant declines to give permission for the data collected to be retained, it will be destroyed.

It is also possible that patients may develop an upper respiratory tract infection and as a result the subjects will be withdrawn. If this occurs, then the participant will be offered a re-screen after 4 weeks from the end of symptoms.

The study may be terminated if there is a determination of futility.

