### **5. Study Design**

#### **5.1. Design**

This is a 9-visit randomized, double-blind, placebo controlled, parallel group study evaluating the effectiveness of 4 doses of mepolizumab for the treatment of refractory chronic cough in patients with eosinophilic airways disease (Figure 1). We plan to complete 15 subjects in each arm of the clinical trial. The duration of intervention will be 12 weeks, during which

subjects will receive 4 doses at days 0, 28, 56 and 84. The effects of mepolizumab on objective cough frequency will be tested at week 14, 2 weeks following the last dose of mepolizumab/placebo.

**Figure 1.** Study flow diagram detailing the study visits and procedures per visit per subject following enrolment.

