22. Women of childbearing potential (WOCBP) must not be actively seeking pregnancy, and must use an effective form of birth control (confirmed by the Investigator). Effective forms of birth control include: true sexual abstinence, a vasectomized sexual partner, Implanon, female sterilization by tubal occlusion, any effective IUD intrauterine device/IUS levonorgestrel Intrauterine system, Depo-Provera™ injections, oral contraceptive, and Evra Patch™ or Nuvaring™. WOCBP must agree to use an effective method of birth control, as defined above, from enrolment, throughout the study duration and within the 8 treatment weeks. They must demonstrate a negative serum pregnancy test at screening and demonstrate a negative urine pregnancy test immediately before

each dose of study drug or placebo. Women not of childbearing potential are defined as women who are either permanently sterilized (hysterectomy, bilateral oophorectomy, or bilateral salpingectomy), or who are postmenopausal. Women will be considered postmenopausal if they have been amenorrheic for 12 months prior to the planned date of randomization without an alternative medical cause. The following age-specific requirements apply:

- i. Women <50 years old would be considered postmenopausal if they have been amenorrheic for 12 months or more following cessation of exogenous hormonal treatment and follicle stimulating hormone (FSH) levels in the postmenopausal range.
- ii. Women ≥50 years old would be considered postmenopausal if they have been amenorrheic for 12 months or more following cessation of all exogenous hormonal treatment.

23. Male patients not using an acceptable method of contraception. All male patients who are sexually active must agree to use an acceptable method of contraception (condom with or without spermicide, vasectomy) from the first dose of study drug until their last dose.

24. Use of angiotensin-converting-enzyme inhibitors

25. Use of immunosuppressive medication (including but not limited to: methotrexate, cyclosporine, azathioprine, intramuscular long-acting depot corticosteroid, oral corticosteroid, or any experimental anti-inflammatory therapy) within 3 months prior to the date informed consent is obtained

26. Use of any other biological within 4 months or 5 half-lives prior to randomization, whichever is longer.

27. Any centrally acting medication within the last 2 weeks which in the view of the investigator could influence the coughing\*

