#### *Risk of contracting COVID-19 infection during study participation*

As long as the COVID-19 pandemic is ongoing, there is a risk of contracting a SARS-CoV-2 infection during the time period of study participation. Participants will be asked about

symptoms and risks of COVID-19 infection prior to each study visit and on the day of the study visit. Participants who are at high risk will be asked to have a COVID-19 test performed at a local public health lab and must have received a negative test prior to attending the study site. Participants will be asked further information regarding symptoms suggestive of COVID-19 infection as part of the screening visit and subsequent visits (as applicable in accordance with guidance from the relevant regional and local public health authorities). Participants must not have had a positive test within 2 weeks of the screening visit. If a participant received a COVID-19 positive test during study participation, the investigator will have to decide whether remaining in the study is compatible with participant’s and site personnel’s safety and well-being.

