### 9. Statistical Plan

#### 9.1. Sample Size Estimation

It is assumed that 60 subjects will be screened to randomize 30 subjects, and 15 will be randomized to complete each treatment arm in 1:1 ratio. This is a proof-of-concept study investigating the effectiveness of mepolizumab on objective cough rates in patients with

eosinophilic asthma or NAEB. As such, no formal power calculation can be currently performed. The sample size is therefore based on previous similar pilot studies using cough monitoring as an endpoint (36, 37).

With 15 patients per arm, this study will have 80% power with an alpha of 5% to detect an estimated 20% greater reduction in 24hr cough frequency compared with the placebo arm, assuming a log standard deviation of 0.60. A clinically relevant reduction in cough frequency of 20% was established following a recent phase 3 studies of gefapixant in refractory chronic cough which showed a 20% reduction over placebo as significant (38). The data from this study will be used to estimate the sample size required for any future multi-centre studies.

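### Section 5.14 withdraws and re-screens anyone with a URTI, even after randomisation or dosing, so week-14 values are lost and a second allocation is not ruled out

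*Combined protocol and SAP*

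**What the plan says.** Section 5.14 states that "patients may develop an upper respiratory tract infection and as a result the subjects will be withdrawn" and that "the participant will be offered a re-screen after 4 weeks from the end of symptoms". Neither sentence has a condition on timing, randomisation or dosing.

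Related provisions:

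- **Randomisation and dosing.** Section 5.10.1 randomises after Visit 1; the first dose is at Visit 3. Doses fall on days 0, 28, 56 and 84. (Table 1 counts post-randomisation days from Visit 3.)
- **Primary endpoint.** The effect on cough frequency "will be tested at week 14, 2 weeks following the last dose of mepolizumab/placebo" (Section 5.1); Section 9.2.2 fixes this as day 98, Visit 8.
- **FAS.** Section 9.2.1 requires at least one dose and a 24-hour recording both before and after treatment. The first recording after dosing is at week 8.
- **Sample size.** In Section 9.1, "15 will be randomized to complete each treatment arm in 1:1 ratio". Thirty are randomised and Section 5.1 plans for 15 to complete in each arm, with no dropout allowance.
- **Re-entry.** Exclusion 26 bars "Use of any other biological within 4 months or 5 half-lives prior to randomization, whichever is longer". Exclusion 25 bars immunosuppressive medication "or any experimental anti-inflammatory therapy) within 3 months prior to the date informed consent is obtained".
- **COVID-19.** If the self-assessment before a visit is not clear, "the participant will be asked to contact the research team to reschedule their appointment" (Section 5.11, Questionnaires). After a positive test, "the investigator will have to decide whether remaining in the study is compatible with" the safety of the participant and staff (Section 5.9.1).
- **Asthma exacerbation on treatment.** Section 6.7 allows prednisone and mentions no withdrawal.

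**The concern.** A URTI is a common, short event and the endpoint is measured up to 14 weeks after the first dose. Under the literal rule, someone infected in week 2 and well by week 4 is still withdrawn and never reaches the week-14 recording. The protocol provides no follow-up after withdrawal and no early-termination visit. It allows a repeat recording only for device failure or, at Visit 6, poor quality. Section 9.3 names missing data in its title but gives no rule for it.

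The re-screen offer raises a second question. For someone already randomised, the plan does not say whether the first allocation is kept, whether a new one is drawn, or how many records that person contributes. What is at stake is a complete primary endpoint and an analysis set with one allocation per person.

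**Working it through.** **Plan's own figure.** Section 9.1 gives no URTI or dropout rate; its only related figure is 80% power with 15 per arm. With a 20% reduction (δ = |ln 0.80| = 0.2231), log SD 0.60 taken as natural log, and a two-sided 5% test:

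Power = Φ(δ / (0.60 × √(2/15)) − 1.96) = Φ(1.018 − 1.960) = 17.3%.

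The stated 80% is therefore not reproduced by a plain two-sample comparison. That is a separate matter; the figure is used here only to gauge the effect of losses.

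**Losses under the literal rule.** Assumptions: 5%, 10% or 20% of 30 participants have a URTI, with onset uniform over days 0 to 98, and every one is withdrawn.

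- Lose week 14: 30 × p.
- Also leave the FAS (onset before the week-8 recording ends on day 57): 57/98 = 58% of these.
- Keep a week-8 value but lose week 14: 41/98 = 42% of these.

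| Infected | Lose week 14 | Leave FAS | Keep week 8 only |
|---|---|---|---|
| 5% | 1.5 | 0.87 | 0.63 |
| 10% | 3.0 | 1.74 | 1.26 |
| 20% | 6.0 | 3.49 | 2.51 |

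These are upper limits for the assumed rates, because rescheduling or investigator discretion may apply instead of withdrawal.

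**Power.** Losing 5% or 20% leaves 14.25 or 12 per arm. At SD 0.60, power moves from 17.3% to 16.7% or 14.7%. If the stated 80% is taken at face value (implied SD 0.218), it moves to 78.0% or 70.7%. Keeping 30 week-14 values would need 30/0.95, 30/0.90 or 30/0.80, that is 32, 34 or 38 randomised.

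**Can a person enter twice?** Exclusion 26 concerns other biologicals. Exclusion 25, if blinded study drug counts as experimental anti-inflammatory therapy, delays re-entry by 3 months and then lapses. Neither bars a second allocation. A person withdrawn before day 98 has no week-14 value from the first entry, so re-entry yields at most one day-98 value. Only the last column of the table could give a duplicate, through week-8 data, which Section 9.2.3 uses for secondary endpoints.

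**Losses if dosed participants are followed.** The Visit 8 window is ±7 days, so the week-14 recording can be made up to day 105. Assume symptoms last 3, 10 or 21 days and the recording is made on day 98 or, if later, when symptoms end.

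- Week 14 lost (onset + duration > 105): 0; (98 − 95)/98 = 3%; (98 − 84)/98 = 14% of infected people.
- Recorded within 21 days after symptoms end (end on days 77 to 105): (98 − 74)/98 = 24%; (95 − 67)/98 = 29%; (84 − 56)/98 = 29%.
- Recorded more than 21 days after symptoms end: 74/98 = 76%; 67/98 = 68%; 56/98 = 57%.
- Week 8 can be missed if symptoms outlast its +3-day window, but the latest such end is day 56 + 21 = 77, before day 98. On these assumptions nobody leaves the FAS because of the URTI.

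**The case against.** **URTI cough contaminates the endpoint.** This is the best argument for withdrawal. Section 1.2 says acute cough after a viral infection can last up to three weeks. In an arm of 15, one recording raised 1.5, 2 or 3 times (assumed) shifts the geometric mean by r^(1/15) − 1 = 2.7%, 4.7% or 7.6%. On the log scale, ln(r)/15 divided by 0.2231 is 12%, 21% or 33% of the target effect. This stands as a reason to defer or flag a recording near an infection. It does not justify ending follow-up of someone infected weeks before day 98.

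**The rule was meant for screening.** The 4-week wait resembles exclusion 1, on unresolved URTI symptoms in the last month. That reading is plausible, but Section 5.14 does not state it, and staff following the text would withdraw a dosed participant. If it was the intention, saying so is easy.

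**Other provisions soften the rule.** They do, which is why the counts are upper limits. A reader might infer that the COVID-19 provisions contradict Section 5.14. They have specific triggers and need not conflict with it, but nothing says which governs when the same symptoms fall under both.

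**The numbers are small.** True, and all rest on assumed rates. With 15 per arm, however, each avoidable loss is 1/15 = 6.7% of an arm.

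**Conclusion.** The point holds as a gap in the stated rule. As written, Section 5.14 discards the week-14 value of any dosed participant with a URTI before day 98, and FAS membership if withdrawal precedes the week-8 recording. It also leaves a second randomisation open. For assumed infection rates of 5% to 20%, spread evenly, the upper limits are 1.5 to 6 people without week 14 and 0.9 to 3.5 out of the FAS. The change is worth making because it is cheap and protects the primary endpoint.

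Four stronger readings are not supported:

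- *The primary endpoint would be double-counted.* A withdrawn person has no day-98 value from the first entry, so a duplicate could arise only through week-8 data.
- *Dosed people will be randomised again.* The documents are silent; a second allocation is only not ruled out.
- *Carry-over will distort re-entrants' baselines.* Re-entry requires sputum eosinophils of at least 2% (inclusion 4), and Section 1.2 says mepolizumab lowers them, so people with substantial residual drug are least likely to qualify. Exclusion 25 may add a delay. The documents give no half-life from which to size what remains.
- *The arms would be biased.* No difference in URTI withdrawal is shown. Table 4 has no URTI row; its nearest entry, influenza at 3% against 2%, does not establish one.

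**What to change.** 1. **Limit withdrawal with re-screening to people not yet randomised.** Someone randomised but undosed who is deferred for a URTI keeps the original allocation and repeats the baseline recording before dosing. Each person then has one allocation and one record. State when randomisation occurs, since Section 5.10.1 and Table 1 differ.
2. **Follow dosed participants to week 14, with consent, instead of withdrawing them.** Defer the week-8 recording (Visit 5, ±3 days) or the week-14 recording (Visit 8, ±7 days) within the Table 1 windows. If the window closes first, that recording is missing but the person stays in the study. Whether dosing continues is a clinical decision; report the doses received.
3. **Flag recordings made within about 21 days of URTI symptoms**, matching the three weeks in Section 1.2, and add a sensitivity analysis without them.
4. **Cross-refer Section 5.14 to the COVID-19 provisions** in Sections 5.9.1 and 5.11, so that it is clear which applies.

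**Cost.** One amendment, probably substantial under Section 13.6, and a check of the consent wording. There are no extra visits for dosed participants; someone deferred before dosing repeats one recording. A deferred week-14 recording may fall up to day 105, 21 days after the last dose instead of 14. Visit 8 at its latest is study day 113 + 7 = 120, so Visit 9 would be day 121, beyond its limit of 114 + 3 = 117. Table 1 already contains this mismatch; the amendment should say that Visit 9 follows Visit 8 by 24 hours. A few recordings will be noisier, and the sensitivity analysis will show their influence.
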